Participants will also be asked to use a MEMS cap pill bottle to monitor medications for approximately 8 weeks (from the baseline assessment through the end-of-treatment assessment). We will monitor ONE medication per patient using the criteria adopted by Wu et al. Briefly, if the patient takes any HF medication *twice* a day, this medication will be MEMS-monitored. If all HF medications have the same daily prescription schedule, the β -blocker will be monitored. If the patient does not receive a β -blocker, the ACE inhibitor or the angiotensin receptor blocker will be used instead. If none of these drugs is prescribed, the aldosterone antagonist or statin, or digoxin or diuretic will be monitored. Participants will receive a MEMS bottle at the baseline visit and will be instructed to open it only when they actually take their medication; they will also be trained to keep track of unscheduled lid openings (i.e. refills, accidental openings) in a diary; these events will be removed prior to analysis. After the baseline visit, participants will enter a 30-day run-in for the assessment of baseline adherence. Participants will start using the cap on the day following the baseline visit (=time 0), and the intervention will start 30 days later; this 30-day period will be considered our baseline.

MEMS Caps are designed to be easily opened and closed, and to be very similar in design to pill bottles commonly used commercially. Participants will be asked to review their medication regimen with PI/SRA. Participants will be asked to fill the bottle with their prescribed heart medication selected for monitoring. Prior to use, a study team member will demonstrate appropriate use of the pill bottle and will invite participants to practice opening and closing the containers.

Written instructions will be provided to all participants, including study staff contact information. Participants will be encouraged to contact staff in the event of any questions or concerns. One week following the baseline assessment and initiation of monitoring, study staff will call the participant to ask if there are any questions regarding use of the devices. Any emergent questions will be answered.

4.1.2 Intervention Session + Pill Count Check OR Pill Count Check only (Visit 2)

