STATISTICAL ANALYSIS PLAN

Values-Affirmation + Education Intervention Targeting Medication Adherence in Older Adults With Heart Failure

NCT05575375

8/1/2022

STATISTICAL DESIGN AND POWER

General Approach: Means and standard deviations will be used to describe continuous variables. Frequencies and percentages will be used to describe categorical data. For secondary, baseline descriptive, and exploratory analyses (see below), a p value $< .05$ will indicate statistical significance with a two-tailed test. Assumptions of relevant statistical tests such as assumptions of normality of the data distribution will be checked to ensure sound application and interpretation of inferential tests.

Intent-to-treat analyses will be used (i.e., all randomized participants will be included in analyses).

Analysis of Primary Endpoints: We will examine descriptive statistics (i.e., means, standard deviations, frequencies, percentages) to assess the primary endpoints. Means and standard deviations will be used to describe continuous variables. Frequencies and percentages will be used to describe categorical data.

- 1) Recruitment feasibility will be determined through examination of the percentage of eligible patients who enroll in the study.
- 2) Retention will be calculated as the percentage of individuals who were enrolled and completed both the baseline assessment, monitoring periods, and end-of-treatment assessment. Feasibility of procedures will be defined as achieving a retention rate of 80%.
- 3) Patient acceptance of the intervention will be determined by mean satisfaction ratings rated on self-report measures with Likert-type questions and assessed through open-ended responding. Adequate acceptability will be defined as $\geq 80\%$ endorsement of being at least somewhat satisfied with participation.

Analysis of Secondary Endpoints:

- 1) Self-reported medication adherence. Analysis of covariance (ANCOVA) will be used to examine differences in self-reported adherence between groups at end-of-treatment.
- 2) Electronically-monitored medication adherence measured the number of days $\geq 80\%$ of prescribed doses were taken. ANCOVA will be performed to examine differences in each outcome between groups at end-of-treatment.
- 3) Additional secondary analyses will use ANCOVA to examine differences in health-related quality of life, self-efficacy, perceived stress, affect and medication-related attitudes between groups at end-of-treatment.

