All analyses of secondary endpoints will be performed with and without adjustment for covariates and baseline scores on the endpoint of interest to control for potential confounders.

Baseline Descriptive Analyses:

Descriptive statistics including means, standard deviations, frequencies, and percentages, will be calculated to characterize demographic, medical, and baseline psychosocial variables. Non-completers and completers will be compared using independent t-tests and chi-squared tests to assess for any differences in baseline characteristics. T-tests and chi-squared tests will also be used to assess differences in demographics and baseline medical and psychosocial characteristics between groups.

There will be no planned interim analysis in this small pilot study.

Exploratory analyses will also examine potential mechanisms of action that warrant examination in a subsequent fully-powered efficacy trial through testing of potential mediators (e.g., changes in self-efficacy, perceived stress, affect, or medication related-attitudes).

To assess potential mediators, multivariate regression analyses will be performed. The direct effects of the treatment condition on the mediator of interest (e.g., self-efficacy, perceived stress, affect, or medication-related attitudes), will be calculated using univariate linear regression. Next, the association between the mediator of interest on medication adherence will be calculated using a linear regression model that includes treatment condition and the mediator of interest as predictors of adherence (dependent variable). Coefficients from

these models will be used to test the indirect effect by the delta method (Sobel test). Mediation analyses will be performed with and without adjustment for covariates and baseline adherence to control for potential confounders.

Potential moderators (e.g., depressive symptoms, social support) will also be tested on an exploratory basis to assist in identifying potential moderators that warrant future study. To assess potential moderators, an interaction term will be created between the variable of interest and the study condition (intervention versus control group assignment) and entered as a predictor in a multivariate regression analysis.

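### The only planned test of mediation is the Sobel test, which is conservative for small-to-moderate paths at n = 40 to 50; a joint test of the same two regressions would miss fewer candidate mediators (minor).

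*SAP*

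**What the plan says.** The mediation plan stands in the last part of the SAP, after Baseline Descriptive Analyses. Its purpose is given as follows: "Exploratory analyses will also examine potential mechanisms of action that warrant examination in a subsequent fully-powered efficacy trial", to be done through "testing of potential mediators (e.g., changes in self-efficacy, perceived stress, affect, or medication related-attitudes".

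Two linear models are planned: the mediator on treatment condition (path a), and adherence on treatment condition plus the mediator (path b). Coefficients from "these models will be used to test the indirect effect by the delta method (Sobel test". No joint-significance test, bootstrap or other interval for the indirect effect appears in either document. The only variation is in the models, not in the test: "Mediation analyses will be performed with and without adjustment for covariates and baseline adherence to control for potential confounders".

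The threshold comes from General Approach: "For secondary, baseline descriptive, and exploratory analyses (see below), a p value $< .05$ will indicate statistical significance with a two-tailed test". The SAP does not say what happens to a mediator that misses this threshold.

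**The concern.** The Sobel test treats the product of two estimated coefficients as if it were normally distributed. With small-to-moderate paths in a sample of about 50, that product is skewed and heavy-tailed, and the test's error falls well below the 5% the plan allows. A screen meant to find leads for a later trial then gives up power without stating a reason. The two regressions already planned contain what is needed for a sharper test at the same nominal level.

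At stake is the yield of an exploratory screen. The primary endpoints are feasibility and acceptability, summarised descriptively, and do not depend on it.

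**Working it through.** **Inputs from the documents**
- Randomised: 25 + 25 = 50 (Protocol 1, Study Design).
- Two-tailed 0.05 for exploratory analyses (SAP, General Approach).
- Path a has n − 2 residual df and path b has n − 3 (unadjusted models as described in the SAP).
- n = 40 is an assumption: 0.80 × 50, from "Feasibility of procedures will be defined as achieving a retention rate of 80" percent.

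The plan gives no figure for mediation, so there is none to reproduce.

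**Step 1: algebra, no path sizes assumed.** The first-order delta-method statistic is

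z = ab / √(a²·SE_b² + b²·SE_a²).

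Dividing through by SE_a·SE_b gives z = t_a·t_b / √(t_a² + t_b²), which is smaller in size than both t_a and t_b. Put both paths exactly at two-sided p = 0.01:

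| n | t_a | t_b | Sobel z | Sobel p |
|---|---|---|---|---|
| 40 | 2.712 | 2.715 | 1.919 | 0.055 |
| 50 | 2.682 | 2.685 | 1.897 | 0.058 |
| 1,000 | 2.581 | 2.581 | 1.825 | 0.068 |

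This example comes from the formula, not from the small sample. For equal paths to reach z = 1.96, each needs t = 1.96 × √2 = 2.772, which is p of about 0.0086 (n = 40) or 0.0079 (n = 50). A t reference for the ratio gives p = 0.063 to 0.064, and the Aroian variance 0.063 to 0.067. The Goodman variance gives 0.047 to 0.049, but the SAP names the Sobel form.

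**Step 2: error and power by simulation.** Settings: 20,000 to 40,000 trials per scenario, equal arms, no direct effect, normal residuals with SD 1, regressions as in the SAP. Here a is the arm effect on the mediator in SD units and b is the mediator–adherence slope. All path sizes are assumptions. Entries are Sobel vs joint rule (both paths p < .05).

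| Scenario | n = 40 | n = 50 |
|---|---|---|
| Error, a = b = 0 | near 0% vs 0.2% | near 0% vs 0.2% |
| Error, a = 0, b = 0.5 | 1.4% vs 4.0–4.1% | 1.8–1.9% vs 4.3–4.4% |
| Power, a = b = 0.2 | 0.3% vs 1.9–2.0% | 0.5% vs 2.7% |
| Power, a = b = 0.3 | 1.6% vs 6% | 2.5–2.6% vs 9% |
| Power, a = b = 0.5 | 15% vs 27–28% | 23–24% vs 37% |
| Power, a = 0.8, b = 0.4 | 26–27% vs 45–46% | 40% vs 60% |
| Power, a = 1.2, b = 0.8 | 93% vs 95% | 98% vs 98% |

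Ranges within a cell are simulation noise between runs. Under normal residuals the joint rule's true error cannot exceed 5%, because the t test of whichever path is null must itself reject. The Sobel test is not strictly bounded: with a = 0 its error was 5.1–5.3% at b = 1.5 and about 5.5–5.7% with a still larger b.

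**Step 3: does the pattern survive a less tidy outcome?** One adherence outcome is a bounded count: "Electronically-monitored medication adherence measured the number of days" meeting a dose threshold. Monitoring is planned "to monitor medications for approximately 8 weeks (from the baseline assessment through the end-of-treatment assessment"), of which 30 days are run-in, so 8 × 7 − 30 = 26 days remain. Protocol 1 allows 8–10 weeks per participant, so the count could run up to 10 × 7 − 30 = 40 days. Only 26 days was simulated. There the joint rule gained 6–20 points for a 0.5–0.8 and b 0.3–0.5, with b on a logit scale and so not comparable with the table. With three covariates and a normal outcome the gain was 12–20 points (a 0.5–0.8, b 0.4–0.5).

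**The case against.** The Sobel test is a recognised, prespecified choice, and nothing in the documents contradicts it. The analysis is exploratory in a small pilot, both path p-values will be visible, and the example is borderline: paths at p = 0.005 and 0.01 give Sobel p = 0.045 (n = 40) or 0.047 (n = 50) and are flagged. A strict screen can also be defended, because the SAP has no multiplicity control and repeats every mediation model with adjustment. All of this stands, and it keeps the point minor. It does not remove the power loss, and the SAP does not say that the strictness is intended.

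Four stronger readings are tempting and are not supported.
- A reader might infer that mediators with Sobel p ≥ .05 will be discarded. The SAP defines statistical significance but states no such rule, so missed candidates follow only if the team screens strictly on that p-value.
- A reader might infer that the two paths are themselves called non-significant. Each regression would still report p = 0.01; only their product is called non-significant.
- A reader might infer that the Sobel test can never inflate false positives. Its error can slightly exceed 5% when one path is very large.
- A reader might infer that the change would make the mediation analysis adequately powered. At a = b = 0.3 the joint rule still has only about 6–9% power.

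**Conclusion.** The point holds as a minor, inexpensive improvement. The p-values of 0.055 and 0.058 follow from the formula, the unadjusted models and a normal reference, with no path sizes assumed. The power gap of about 12–20 points at a = b = 0.5 and at a = 0.8, b = 0.4 depends on assumed path sizes and, for n = 40, on retention at the plan's 80% threshold. It shrinks to about 2 points or less at a = b = 0.2 and to 0–2 points at a = 1.2, b = 0.8. Power is modest under either method for small-to-moderate paths, so a non-significant mediation result from this trial says little about whether a mechanism exists.

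**What to change.** In the SAP's mediation paragraph, replace the Sobel sentence with, for example:

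> An indirect effect will be flagged when both planned path coefficients reach p < .05 (joint significance). The product of the coefficients will be reported with a Monte Carlo or percentile-bootstrap 95% interval as a description of size and precision, in the unadjusted and the adjusted models. An interval that includes zero is not evidence that a mechanism is absent.

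The SAP should name one of the two intervals, with the number of draws (at least 5,000) and a fixed seed.

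**Cost.** A rewritten SAP sentence and a few lines of code; no new data, visits or participants.

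**Downside: more false leads.** Take the four named mediators and two adherence outcomes, 4 × 2 = 8 tests (an assumption), at a = 0, b = 0.5. Expected false leads rise from 8 × 1.4–2.7% = 0.11–0.22 to 8 × 4.1–4.9% = 0.33–0.39, before the adjusted repeats. The upper ends come from a smaller outcome residual SD of 0.866.

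**Interval behaviour.** The intervals can run above 5% error when one path is null and the other very large: up to 6.0% for Monte Carlo and 7.2% for the bootstrap at a = 1.6, b = 0, n = 50. That is why the joint rule, not the interval, should decide what is flagged.

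If the team prefers the stricter Sobel screen, one sentence saying that this is deliberate would be enough.

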1 STUDY DESIGN

This research will examine the initial feasibility and acceptability of a values-affirmation, education, and skills-training intervention targeting heart failure (HF) medication adherence using the NIH Stage Model for Behavioral Intervention Development (Onken et al., 2014).

Design: This study is a Stage 1B trial and will use a randomized controlled trial design. Participants will be randomized 1:1 basis to the Values-affirmation Intervention condition (n = 25) or Usual Care (n = 25).

Setting: Study assessments and intervention delivery will occur either at the participant's home or The Miriam Hospital's Center for Behavioral and Preventive Medicine (CBPM). The location will be determined by participant preference. Data management and analysis will be housed at CBPM.

Study Duration: Study duration is estimated to be 21-24 months from the time of enrollment of the first subject to completion of data collection. Individual participants will complete the protocol within 8-10 weeks from the time of the baseline visit until the end-of-treatment assessment. Study completion is defined as completion of the baseline and end-of-treatment assessments, intervention content, and medication monitoring period.

Sample: 50 older adults with HF, ages 50 and older, who are enrolled in a CR program in Providence, Rhode Island will be recruited. We aim to recruit a sample that is 51% women and 30% individuals who identify as a NIH-defined racial or ethnic minority.

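### The mediation plan does not settle whether the mediator is a final or a change score and does not name its own baseline for adjustment, so indirect effects can be biased in either direction

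*SAP*

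**What the plan says.** The SAP's exploratory paragraphs announce "testing of potential mediators (e.g., changes in self-efficacy, perceived stress, affect, or medication related-attitudes". The model description that follows no longer mentions change:

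- The treatment-to-mediator path (path a) "will be calculated using univariate linear regression", so treatment is the only predictor.
- The mediator-to-adherence path (path b) comes from a "linear regression model that includes treatment condition and the mediator of interest as predictors of adherence (dependent variable".
- The coefficients are then used to "test the indirect effect by the delta method (Sobel test".

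On adjustment, the text reads: "Mediation analyses will be performed with and without adjustment for covariates and baseline adherence to control for potential confounders". The covariates are not listed, and adherence is the only variable whose baseline is named.

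The SAP treats the secondary endpoints differently. Those are analysed "with and without adjustment for covariates and baseline scores on the endpoint of interest to control for potential confounders", so each outcome's own baseline is named there. Protocol sections 4.1.1 and 4.1.3 list self-efficacy, perceived stress and affect at both Visit 1 and Visit 3, so baselines for these three mediators will exist. Neither section lists a measure under the name of medication-related attitudes.

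**The concern.** Randomization protects path a but not path b. People who are more confident, or less stressed, may adhere better throughout, whatever the intervention does. If the mediator enters as an end-of-treatment score without its baseline, path b can absorb that stable difference. Multiplied by a real treatment effect on the mediator, it gives an indirect effect where none exists. Path a also loses precision when a correlated baseline is left out.

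These analyses are meant to suggest which mechanisms deserve study in a larger trial, and the SAP's General Approach applies a significance threshold to them. A screen that can flag or miss mechanisms because of the form of the model serves that purpose poorly.

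**Working it through.** **Inputs from the documents.** The sample is "Values-affirmation Intervention condition (n = 25) or Usual Care (n = 25" (Protocol, section 1). For exploratory analyses, "a p value $< .05$ will indicate statistical significance with a two-tailed test" (SAP, General Approach). The models are the two regressions and the Sobel test described above. The plan gives no effect size, correlation or power for mediation, so there is no figure to reproduce.

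**Assumptions.** a is the treatment shift in the mediator, in SD (0, 0.3, 0.5 or 0.8). b is the true mediator effect on adherence (0 or 0.4). ρ is the mediator's baseline-to-final correlation (0.6; also 0.4 and 0.8). g is the effect of the stable trait on adherence (+0.5, 0 or −0.5).

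**Step 1: closed form, stable-trait model.** Let M0 = U + e0, M1 = aT + U + e1 and Y1 = bM1 + gU + other, with Var(U) = ρ and Var(e) = 1 − ρ. Within arms, the path-b coefficient is:

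- final score, no baseline: b + gρ
- final score plus baseline mediator: b + gρ/(1 + ρ)
- change score, no baseline: b(1 − ρ)/[2(1 − ρ)] = b/2

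With b = 0, g = 0.5 and ρ = 0.6 these are 0.30, 0.1875 and 0. Multiplied by a = 0.8, the spurious indirect effects are 0.24, 0.15 and 0. Simulation (4,000 runs) gave 0.238, 0.149 and 0.000. Unadjusted at ρ = 0.4 and 0.8, the formula gives 0.16 and 0.32; simulation gave 0.160 and 0.321.

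**Step 2: the planned adjustment and the alternatives.** Mean indirect effect at a = 0.8 and ρ = 0.6, with Sobel rejection rates in the first row:

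| Setting | Truth | Final, unadjusted | Final + baseline adherence | Final + both baselines | Change, unadjusted | Change + baseline adherence |
|---|---|---|---|---|---|---|
| b = 0, g = +0.5 | 0 | 0.238 (24.3%) | 0.128 (7.8%) | 0.083 (4.5%) | 0.000 (1.8%) | 0.001 (1.5%) |
| b = 0.4, g = +0.5 | 0.320 | 0.565 | 0.380 | 0.404 | 0.162 | 0.264 |
| b = 0.4, g = 0 | 0.320 | 0.320 | 0.247 | 0.320 | 0.158 | 0.239 |
| b = 0.4, g = −0.5 | 0.320 | 0.080 | 0.100 | 0.239 | 0.163 | 0.235 |

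Bias goes both ways. Using both baselines is not closest in every row (0.404 against 0.380 in the second) and leaves 0.083 where the truth is 0, because M0 measures U with error.

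**Step 3: false positives with more stable measures.** Here 70% of each measure is stable, the stable parts correlate 0.4 to 0.8, a = 0.8 and b = 0. Final-score rejection rates were 22–73% unadjusted, 4–29% with baseline adherence and 4–12% with both baselines. Change scores gave 1.7–2.4% unadjusted and 1.6–2.4% with baseline adherence. The problem needs a sizeable shift. With baseline adherence only, and stable-part correlations of 0.4/0.6/0.8, final scores gave 1.1/3.0/11% at a = 0.5, 0.5/1.2/3.8% at a = 0.3, and under 1% at a = 0.

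**Step 4: autoregressive model.** Stability is 0.7 for both measures, the baseline mediator and baseline adherence correlate at r = 0.3 to 0.5, and the part of M1 not predicted by M0 (variance 1 − 0.49 = 0.51) drives adherence with b = 0.4.

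- Final + baseline adherence: 0.4 × 0.51/(1 − 0.49r²) = 0.204/0.956 = 0.21 at r = 0.3 and 0.204/0.878 = 0.23 at r = 0.5. Simulated 0.21–0.23, power 21–25%.
- Final + both baselines: simulated 0.39–0.40, power 59–60%. This model is the one that the two-baseline regression fits exactly, so it favours that analysis.
- Change, unadjusted: (0.204 − 0.3 × 0.7 × r)/(0.09 + 0.51) = 0.141/0.60 = 0.235 and 0.099/0.60 = 0.165. Simulated 0.17–0.23. With baseline adherence, 0.34–0.35.
- Change, unadjusted, b = 0: −0.21r/0.60 = −0.105 and −0.175. Simulated −0.11 to −0.17, where the truth is 0.

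**Step 5: path a.** SE = √(2/25) = 0.283. With a baseline correlating 0.6 it is 0.283 × √(1 − 0.36) = 0.226; at 0.7 it is 0.283 × √(1 − 0.49) = 0.202. At correlation 0.6, power Φ(a/SE − 1.96) rises from 42% to 60% for 0.5 SD and from 81% to 94% for 0.8 SD.

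**The case against.** The strongest reply is that the SAP introduces the mediators as changes, and a change score uses the baseline. Read that way, trait-driven false positives are about 2%, lower than the two-baseline analysis can promise in the same model. This stands as far as it goes. A reader might infer that the plan never uses the mediator's baseline, but the documents leave that open. The change reading still does not rescue the plan: in Step 1 an unadjusted change score recovers only half of b, and in Step 4 it is attenuated and can show a negative effect where there is none.

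Second, the unlisted covariates might include the mediator's baseline. It is therefore wrong to say that the plan adjusts for baseline adherence and nothing else. But an unlisted covariate is not a prespecified one, and the SAP does name own baselines for the secondary endpoints.

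Third, a reader might conclude that real mechanisms will be underestimated. That is not general: the table shows overestimation, no bias and underestimation, depending on the trait effect and the adjustment.

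Fourth, the highest false-positive rates belong to the unadjusted version, which the SAP pairs with an adjusted one, and they assume a large shift in the mediator. That is correct. The analysis is also labelled exploratory, and the primary endpoints (Protocol, section 6) do not depend on it.

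**Conclusion.** The concern holds in limited form. The SAP leaves open whether the mediator is a final or a change score and does not name its baseline as a covariate.

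With final scores, a mediator that treatment shifts substantially can be falsely flagged. At an assumed 0.8 SD shift this happened in 4–29% of simulated trials with baseline adherence in the model, against 4–12% with both baselines. At 0.3 SD it was below 4% even with baseline adherence alone. Path a stays unbiased by randomization but loses precision. With change scores, false flags largely vanish under a stable-trait model, but path b can be biased under others.

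It would go too far to say that adding the baseline mediator makes the analysis unbiased. It reduces the trait bias, and some remains when the baseline measures the trait with error. All magnitudes rest on assumed shifts, stabilities and correlations. The weight is modest, since this is an exploratory analysis in a 50-person pilot.

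**What to change.** State in the SAP that the mediator is the end-of-treatment score. For self-efficacy, stress and affect, include the baseline mediator and baseline adherence in both the treatment-to-mediator and the adherence models, and name this as the lead mediation analysis. Once the baseline mediator is in both models, final and change scores give the same treatment-to-mediator and mediator-to-adherence coefficients, so the ambiguity no longer matters. Describe results as associations: residual bias can remain, and the mediator is measured at Visit 3, at the close of the adherence monitoring period.

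The cost is one SAP sentence and one degree of freedom, with no new data for these three mediators. Nominal power is somewhat lower under some patterns. For example, with a = 0.8, b = 0.4, g = +0.5 and ρ = 0.8 it was 60.3% with both baselines against 68.1% with baseline adherence alone, although in that setting the latter tests a coefficient that is itself inflated (0.492 against a true 0.4).
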